Subjects will remain in the study until the clinical confirmatory endpoint of all-cause graft failure is evaluated up to a maximum of 4 years. Graft failure is evaluated by the nephrology EAC. Graft failure, for the purpose of this study, will be defined as 1 or more of the following: (1) institution of permanent dialysis (defined as dialysis treatment >30 days), (2) current transplant nephrectomy, or (3) clinical determination of cessation of kidney graft function and $eGFR_{MDRD} \leq 15 \text{ mL/min/1.73m}^2$. If a subject is discontinued for any reason prior to the Month 6 follow-up Visit, every effort will be made to obtain adverse events (AEs), serum blood urea nitrogen (BUN) and creatinine (Cr) results, $eGFR_{MDRD}$, and a biopsy to send slides and images to the pathology and nephrology EACs for determination of TG and graft function status respectively (see [Table 2](#) for Early Discontinuation Visit procedures). If a subject is discontinued for any reason prior to the end of the study at 4 years, every effort will be made to obtain AEs, serum BUN and Cr and $eGFR_{MDRD}$ results to send to the nephrology EAC for determination of graft function status (see [Table 2](#) for End of Study Visit procedures).

There will be 3 analyses (2 interim, 1 final) of proportions of subjects with all-cause graft failure, at approximately 50% (~26 events), 75% (~39 events), and 100% (~51 events) of the study data. Following the Month 6 evaluation, subjects will enter a long-term follow-up stage of the protocol, which will include allograft function evaluations every 6 months up to a maximum of 4 years. The duration of the study will be event driven, and is based upon an assumption that there will be approximately 51 all-cause graft failures. The study will continue until 51 such events are accrued and adjudicated by the nephrology EAC. However the maximum amount of time each subject will be followed in the study will be 4 years post initial treatment with investigational product. See Section 9.5.2 for additional details.

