9.8.2 Secondary Efficacy Endpoints

9.8.2.1 Key Secondary Efficacy Endpoint

The key secondary endpoint is defined as the proportion of subjects with all-cause graft failure (ie, return to permanent dialysis and/or removal of the transplanted kidney and/or clinical determination of cessation of graft function) at 4 years following treatment of the initial qualifying AMR episode. The FAS population will be used to report the efficacy data for all-cause graft failure. Subjects who do not have the key secondary efficacy endpoint assessed post-dose will be assigned as failures.

The proportion of subjects with all-cause graft failure will be summarized by treatment group. Subjects with an assessment of all-cause graft failure or who drop out due to graft failure will be included in the hypothesis testing.

The test statistics and boundary values for decision making at the 3 analyses (2 interim and 1 final) will be specified in the SAP.

The null hypothesis for the proportion of subjects with all-cause graft failure post-treatment will be tested at the overall accumulative alpha level of 0.025 (1-sided test). This hypothesis will only be tested if testing for the primary endpoint of new or worsening TG at 6 months of initiation of treatment is statistically significant.

A number of sensitivity analyses will be performed to assess any impact on the key secondary endpoint results, inference, and conclusions due to missing data. In addition, descriptive analyses on the key secondary endpoint will be provided in selected subgroups.

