## 10.2 Key Secondary Efficacy Endpoint(s) and Analysis

The key secondary endpoint is defined as the proportion of subjects with all-cause graft failure at 4 years following treatment of the initial qualifying AMR episode. The graft failure is defined as 1 or more of the following: (1) institution of permanent dialysis, (2) current transplant nephrectomy, or (3) clinical determination of cessation of kidney graft function in any subject that had received a pre-emptive kidney transplant prior to starting dialysis. The FAS will be used for analyzing the key secondary endpoint. Subjects who discontinued prior to 4 years (i.e. Month 48) will be considered 'missing assessment for graft failure at 4 years' and assigned as failures.

The hypothesis of the key secondary endpoint will only be tested if the testing for the primary endpoint of new or worsening TG at 6 months is statistically significant.

The key secondary analysis specified below will be performed based on the FAS. As a sensitivity analysis, the key secondary analysis will be also performed based on Per-protocol Analysis Set-2.

The key secondary endpoint will be presented as the proportion of subjects with all-cause graft failure, and their difference between treatments ( $\Delta_{Cinryze-Placebo}$ ) is defined as follows:

$$\Delta_{Cinryze-Placebo} = \Pi_{Cinryze} - \Pi_{Placebo}$$

Where  $\Pi_{Cinryze}$  is the proportion of all-cause graft failure post-treatment in the CINRYZE group and  $\Pi_{Placebo}$  is the proportion of all-cause graft failure post-treatment in the placebo group.

The analysis will employ a type I error rate of 0.025 to test null hypothesis:

$$H_0 : \Pi_{Cinryze} - \Pi_{Placebo} \geq 0$$

Against the 1-sided alternative:

$$H_a : \Pi_{Cinryze} - \Pi_{Placebo} < 0$$

The key secondary endpoint will have 3 analyses (2 interim and 1 final), at approximately 50% (~26 events), 75% (~39 events) and 100% (~51 events) of the targeted all-cause graft failure. The purpose of the interim analyses is to consider early stopping of the study for claiming of efficacy.

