The difference between treatments will be evaluated by a Fisher's Exact test. If the p-value from the test is  $\leq 0.0030$  at first interim analysis (~50% of events), or  $\leq 0.0075$  at the second interim analysis (~75% of events), or  $\leq 0.0221$  at the final analysis (~100% of events), it will be concluded that CINRYZE is efficacious based on the proportion of subjects with all-cause graft failure and the result will serve as confirmatory evidence of clinical benefit based on all enrolled subjects.

Sensitivity analyses will be done at final analysis by using multiple imputation (MI) assuming missing at random (MAR) to assign missing key secondary endpoint and/or by using Cochran–Mantel–Haenszel (CMH) test for treatment effect. The CMH model will assess the treatment effect with controlling for (1) donor characteristic (living vs deceased), (2) baseline AMR severity (severe vs mild to moderate), and possibility (3) time to onset of qualifying AMR from current transplant ( $>100$  days vs  $\leq 100$  days) if degree of freedom allows. All the sensitivity analyses defined below will be based on the FAS.

	Statistical Test	Logic to assign the missing assessments for graft failure at 4 years (i.e. discontinued prior to 4 years)
Key Secondary Analysis Model	Fisher's Exact	Assign failure for subjects who discontinued prior to 4 years.
Sensitivity analysis 1	Fisher's Exact	MI for subjects who discontinued prior to 4 years.
Sensitivity analysis 2	CMH	Assign failure for subjects who discontinued prior to 4 years.
Sensitivity analysis 3	CMH	MI for subjects who discontinued prior to 4 years.

For multiple imputation for the key secondary endpoint, a monotone missing pattern will be assumed. The prediction model will consider treatment group, , AMR severity baseline, donor characteristic as factors with available post-dose eGFR results incorporated. The imputation seed will be 83789524 and number of imputations will be set as 100.

For sensitivity analysis 1, multiple imputation will be used to impute the key secondary endpoint outcome for all subjects who discontinued prior to 4 years. The p-values from Fisher's Exact tests will be computed for each imputed dataset and transformed to  $\chi^2$ -distribution with  $df = 2$  using Fisher's transformation as:

$$\Psi^{(m)} = -2 \log(p^{(m)}) \sim \chi_2^2$$

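### Key secondary sensitivity analyses 1 and 3 impute every subject who left before Month 48, so a graft failure already adjudicated before or at departure is redrawn as if unknown

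*SAP*

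**What the plan says.** SAP 10.2 defines missingness for the key secondary endpoint by discontinuation. Subjects who left before Month 48 "will be considered 'missing assessment for graft failure at 4 years' and assigned as failures". The table of sensitivity analyses carries the same equation in its column heading, and its entry for analyses 1 and 3 reads "MI for subjects who discontinued prior to 4 years". The text for both analyses then says that "multiple imputation will be used to impute the key secondary endpoint outcome for all subjects who discontinued prior to 4 years". The imputation model uses treatment group, baseline AMR severity and "donor characteristic as factors with available post-dose eGFR results incorporated". Known graft failure is not listed as a reason to keep an outcome.

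The protocol expects graft failure to end participation for some subjects. Section 3.1 and the Synopsis state: "Subjects will remain in the study until the clinical confirmatory endpoint of all-cause graft failure is evaluated up to a maximum of 4 years". Section 9.8.2.1 states: "Subjects with an assessment of all-cause graft failure or who drop out due to graft failure will be included in the hypothesis testing".

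Elsewhere the SAP treats such failures as observed. Per-protocol Set-2 (SAP 4.6) accepts a failure within 4 years as an assessed outcome. The time-to-event rules in SAP 10.3 use the failure date on the CRF and censor only those who left without graft failure.

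**The concern.** Graft failure as defined here (permanent dialysis, nephrectomy, or clinically determined cessation of function) is a lasting state. A subject adjudicated as failed at Month 14 who then leaves is a known failure at Month 48. The rule in SAP 10.2 deletes that outcome, fits the imputation model without it, and draws a replacement that may be a non-failure.

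Analyses 1 and 3 are the only imputation-based checks on whether missing data drive the graft-failure result. A check that removes observed events understates the failure rate in both arms. It removes more events from the arm that has more of them, and it may fail to support a real effect for reasons unrelated to missing data.

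**Working it through.** **Inputs.** SAP 2.5 and Protocol 9.6 give failure rates of 68% (placebo) and 34% (CINRYZE), 100 evaluable subjects allocated 1:1, 90% power at one-sided 0.025, 10% drop-out, 112 randomized and 51 events. SAP 10.2 gives the final one-sided threshold of 0.0221. The share f of failures that end participation is not given, so it is an assumption shown as a range.

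**The plan's own figures reproduce.**
- Combined rates: 1 − 0.36 × 0.88 = 68.3% and 1 − 0.75 × 0.88 = 34.0%.
- The two-proportion formula with continuity correction gives 50 per arm. Exact Fisher power at 50 per arm is 91.5% at 0.025.
- 100/0.9 = 111.1, rounded up to an even 112.
- Events: 50 × 0.68 + 50 × 0.34 = 34 + 17 = 51.

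**Effect of the rule.** Let p be an arm's true failure rate. If a share f of failures is set to missing and imputed within arm under MAR without eGFR, the imputed rate is

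(1 − f)p / (1 − fp).

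For f = 0.25 this is 0.51/0.83 = 61.4% on placebo and 0.255/0.915 = 27.9% on CINRYZE.

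| Share f | Events redrawn (51 × f) | Placebo | CINRYZE | Difference (points) | Power of analysis 1 |
|---|---|---|---|---|---|
| 0 (failures kept) | 0 | 68.0% | 34.0% | 34.0 | about 91% |
| 10% | 5.1 | 65.7% | 31.7% | 34.0 | about 90% |
| 20% | 10.2 | 63.0% | 29.2% | 33.8 | not simulated |
| 25% | 12.8 | 61.4% | 27.9% | 33.6 | about 83% |
| 50% | 25.5 | 51.5% | 20.5% | 31.0 | about 74% |

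Power comes from simulating Fisher's test, the Wilson-Hilferty transformation and Rubin pooling at 0.0221. It used 50 per arm, 400 trials per row, 50 imputations (the SAP plans 100) and no other drop-out. The simulation standard error is about 1.5 points near 90% (√(0.9 × 0.1/400)) and 2.2 points near 74%.

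**Direction.** The imputed odds in an arm are (1 − f)p/(1 − p). With the same f in both arms the factor (1 − f) cancels, and the odds ratio stays at (0.68/0.32)/(0.34/0.66) = 4.125 for any f below 100%. At f = 100% no failures remain to fit the model.

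**The case against.** **A programmer would read missing narrowly.** SAP 10.2 describes the aim as "using multiple imputation (MI) assuming missing at random (MAR) to assign missing key secondary endpoint", and a known failure is not missing in the ordinary sense. That is a sensible intention, but the section defines missing as discontinued, both in the text and in the table heading. SAP 10.1 (sensitivity analysis 6) also expressly imputes subjects who had a TG reading at discontinuation, so imputing over available data is not foreign to this SAP.

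**Few failures may be affected.** A subject who stays until graft failure is evaluated might be counted as having completed, and others may stay on visits after failure. The plan assumes only 10% drop-out: 0.10 × 112 = 11.2, and 11.2/51 = 22% of events even if every drop-out were a graft failure. This largely stands. The lower rows of the range are the more plausible ones, and little is lost at 10%. It is not a strict cap, because the drop-out allowance may have been meant only for subjects without an outcome.

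**Post-dose eGFR is in the model.** This stands in part. An eGFR of 15 or below is an element of the failure definition, and eGFR is scheduled at discontinuation, so many departed failures would probably be redrawn as failures. The SAP does not specify the term, the rates above omit it, and even a good predictor turns a certain event into a probability.

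**A reader might infer that these analyses could contradict a true result.** The documents do not support that. With equal leaving the odds ratio and direction are preserved. A reversal would need leaving to differ by arm, and nothing in either document indicates that it would.

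**Conclusion.** The rule in SAP 10.2 for sensitivity analyses 1 and 3 is wrong as written: it redraws outcomes that are known. The harm is understated failure rates in both arms, lost power and, at larger shares, a smaller absolute difference. At shares of 10% to 25% the difference barely moves (34.0 to 33.6 points) and power is about 90% to 83%. At 50% the difference is 31.0 points and power about 74%, against about 91% with failures kept. These figures assume the planned rates, 50 per arm, equal leaving in both arms, no other drop-out and no eGFR in the model. Including eGFR would recover part of the loss.

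A reader might also infer that the confirmatory test of the key secondary endpoint is compromised by this rule. It is not: the main analysis and sensitivity analysis 2 assign these subjects as failures, which for them is correct.

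Nor does the point bear on reported results. SAP 17 states that the key secondary analyses will not be conducted after the stop for futility, and SAP 20 marks the two tables concerned (14.2.2.2 and 14.2.2.4) as not produced. This corrects the written plan and leaves the abbreviated report unchanged.

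**What to change.** In SAP 10.2, sensitivity analyses 1 and 3:

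- Keep any adjudicated graft failure up to Month 48 as an observed failure, both in fitting the imputation model and in every imputed dataset. Include failures learned of after discontinuation, since Protocol 4.5 seeks graft status from discontinued subjects through Month 48.
- Impute only subjects who discontinued before Month 48 and whose graft status at Month 48 is unknown.
- Align the table heading and entries with this definition.

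The cost is two sentences in the SAP, the matching table edit and one condition in the imputation program. No new data are needed, because failure dates are already on the CRF and failures are adjudicated.

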### **10.3 Secondary Efficacy Endpoint(s) and Analysis**

Secondary efficacy endpoints from study entry to 6 months are defined as:

- Measurement of renal function (eGFRMDRD) at 6 months
- Change in renal function (eGFRMDRD) from pre-AMR to 6 months
- Change in renal function (eGFRMDRD) from screening to 6 months
- Measurement of proteinuria (spot urine protein, urine creatinine, and urine protein/urine creatinine ratio) at 6 months
- Change in proteinuria (spot urine protein, urine creatinine, and urine protein/urine creatinine ratio) from baseline to 6 months
- Change in histopathology per Banff criteria (Banff 2013 classification) from pre-AMR to 6 months
- Proportion of subjects with all-cause graft failure at 6 months

Secondary efficacy endpoints from study entry to 4 years are defined as:

- Measurement of renal function (eGFRMDRD) and change from pre-AMR baseline and screening at 1, 2, 3, and 4 years following the qualifying AMR episode
- Measurement of proteinuria (spot urine protein, urine creatinine, and urine protein/urine creatinine ratio) and change from screening at 1, 2, 3, and 4 years following the qualifying AMR episode
- Time to all-cause graft failure
- Proportion of subjects with graft failure due to AMR at 4 years
- Time to graft failure due to AMR
- Proportion of subjects with resolution of the qualifying AMR episodes

- Time to resolution of qualifying AMR episodes
- Proportion of subjects alive at 4 years
- Time to all-cause mortality

The proportion of subjects with all-cause graft failure at 6 months, the proportion of subjects with graft failure due to AMR at 4 years, the proportion of subjects with resolution of the qualifying AMR episodes, the proportion of subjects alive at 4 years will be summarized descriptively by treatment group.

Time to all-cause graft failure, time to graft failure due to AMR, time to resolution of qualifying AMR episodes, and time to all-cause mortality for both treatment groups will be summarized by Kaplan-Meier estimates. The difference between treatment groups will be assessed by proportional hazard regression with treatment group, baseline acute AMR severity, and donor characteristic as factors. Hazard ratio and the 95% confidence interval will be summarized.

- Date of graft failure will be captured on CRFs as (1) date of return to or institution of permanent dialysis, or (2) date of transplant nephrectomy, or (3) date of clinical determination. Time to graft failure in months will be calculated as (Date of graft failure – Date of first dose + 1)/30.25. Subjects who have not experienced graft failure but still on-study will be censored at the last date of graft survival assessment; subjects who have completed the study without experiencing graft failure will be censored at the date of study completion; subjects who discontinued the study without graft failure will be censored at the last date of graft survival assessment.
- Time to graft failure due to AMR in months will be calculated as (Date of graft failure due to AMR – Date of first dose + 1)/30.25. Subjects who have not experienced any graft failure and still on-study will be censored at last date of graft survival assessment; subjects who have completed the study without experiencing graft failure will be censored at the date of study completion; subjects who have experienced graft failure due to reasons other than AMR will be censored at the date of graft failure; subjects who discontinued from the study without graft failure will be censored at the last date of graft survival assessment.
- Time to resolution of qualifying AMR episodes will be calculated as (Date of qualifying AMR resolution – Date of first dose + 1)/30.25. Subjects who have not had resolution of qualifying AMR episodes and still on-study will be censored at the date of last visit; Subjects who have completed the study without resolution of qualifying AMR will be censored at the date of study completion; subjects who discontinued from the study without resolution of qualifying AMR will be censored at the date of early discontinuation.
- Time to all-cause mortality will be calculated as (Date of discontinuation due to death – Date of first dose + 1)/30.25. Subjects who are alive and still on-study will be censored

at the date of last visit; Subjects who have completed the study will be censored at the date of study completion; subjects who discontinued from the study but not due to death will be censored at the date of early discontinuation.

Renal function and proteinuria will be evaluated as change from the corresponding baseline value. Proteinuria will be log-transformed before analysis. Summary statistics (mean, SD, median, min, max) will be provided by treatment group and assessment time points. Difference between treatments in change from baseline to 6 months will be assessed by a MMRM model including all available scheduled assessments through 6 months. Differences between treatments in change from baseline from 1 year through 4 years will be assessed by a separate MMRM model. The analysis models will include effects of treatment group, visit, treatment\*visit, baseline acute AMR severity, donor characteristic as well as the corresponding baseline values as covariates. The baseline diabetic status (diabetic vs non-diabetic) may be included in the MMRM model as a factor for graft function and serum creatinine if degree of freedom allows. The baseline\*visit interaction will also be included. An unstructured covariance structure shared across treatment groups will be used to model the within-subject errors. Baseline value for renal function is defined as assessment at screening and pre-AMR, separately, for different analyses. Baseline value for proteinuria is defined as the last measurement prior to the first dose of investigational product during the study.

The renal function, as measured by eGFRMDRD, will be estimated by the Modification of Diet in Renal Disease [MDRD] formula shown below:

$$\text{eGFR} = 175 \times \text{Serum Creatinine}^{-1.154} \times \text{Age}^{-0.203} \times [1.210 \text{ if Black}] \times [0.742 \text{ if female}] \times [0.808 \text{ if Japanese}]$$

[figure not shown]
where Serum Creatinine is from the central laboratory and expressed in mg/dL, and age is expressed in years. Note: Age collected at screening visit will be used for all visits before Month 12 visit and then increase by 1 year at Month 12, by 2 years at Month 24, 3 years at Month 36 and 4 years at Month 48.

Number of subjects with all-cause graft failure at 6 months will be summarized by cause of graft failure and by treatment group for FAS.

Number of subjects with resolution of AMR episodes will be summarized by resolution criteria (Clinical criteria vs. Histopathology vs. both) and by treatment group for FAS. Summary statistics for number of days from the first dose of investigational product to AMR resolution will be provided by AMR episode and treatment group.

#### **10.4 Exploratory Efficacy Endpoint(s) and Analyses**

Exploratory endpoints are defined as:

## 11. SAFETY ANALYSES

The safety analysis will be performed using the Safety Analysis Set, unless specified otherwise. Safety variables include TEAEs, clinical laboratory variables, vital signs, lower extremity exam, and C1 INH antibody variables. For each safety variable, the last value collected prior to the first dose of investigational product during the study will be used as baseline for all analyses of that safety variable.

Summary statistics and changes from baseline to post-baseline for clinical laboratory testing, vital signs, diabetes status, and lower extremity exam by treatment group will be presented. For the clinical laboratory testing results, only the scheduled central lab data will be included in the summary tables. All unscheduled or local lab data will only be provided in the listing.

Number, severity, and causality of AEs will be summarized by treatment group.

Results of C1 INH antibody testing will be reported for individual subjects and summarized as appropriate.

A Final on-Treatment Assessment (FoTA) is defined as the last valid assessment obtained up to 30 days after the last dose of the investigational product during the study.

